13.5.3. Reporting Standards for Pharmacokinetic

Pharmacokinetic Concentration Data	
Descriptive Summary Statistics, Graphical Displays and Listings	
Refer to the GSK Standard PK Display Standard.
 
Refer to the GSK Standard Statistical Display Principle 6.06.1.
 
Note: Concentration values will be imputed as per GUI_51487 for descriptive summary statistics/analysis and summarized graphical displays only.

13.6. Appendix 6: Derived and Transformed Data

13.6.1. General

Multiple Measurements at One Analysis Time Point

 If there are two values within a time window (as per Section 13.3.1) the value closest to the target day for that window will be used. If values are the same distance from the target, then the mean (geometric mean for HIV-1 RNA, arithmetic mean for all other measurement) will be taken. Assessments not chosen for use in summary statistics by this algorithm will still appear in the associated listings. All applicable valid assessments, irrespective of proximity to the target study day, will be used when categorizing values across visits, such as 'maximum grade during the intervention phase' or 'at any time post-baseline', and for any algorithm that has specific rules for which observation to use (e.g. snapshot algorithm, LOCF or CVF identification). Participants having both High and Low values for Normal Ranges at any post-baseline visit for safety parameters will be counted in both the High and Low categories of "Any visit post-baseline" row of related summary tables. This will also be applicable to relevant Potential Clinical Importance summary tables.
Treatment Start Date

 Intervention Phase Treatment Start Date = Earliest date of CAB + RPV oral lead-in entered in the IP exposure eCRF form
Nominal Month 13 Visit Date

 For participants who received Month 13 injection, the nominal Month 13 visit date is defined by the Month 13 injection date. Otherwise, nominal Month 13 visit date is defined by the date of latest Month 13 assessment. For participants who continued into Extension Phase but missed the Month 13 visit, the nominal Month 13 visit date is defined by the last contact date prior to the date of the first nominal extension phase visit (e.g. Month 15, Month 17, etc.).
Study Day

 The Study Day of an event (e.g., lab assessment, vital sign, ECG, start date of AE or HIV associated condition) will be derived as the number of days between the date of the event and the Intervention Phase treatment start date as follows: 
 If date of event \geq start date of study treatment, then 
 Study Day = Date of Event - Intervention Phase Treatment Start Date + 1 If date of event $<$ start date of study treatment, then 
 Study Day = Date of Event - Intervention Phase Treatment Start Date Note that the start date of intervention phase study treatment is on Study Day 1 and the day before this is Study Day -1; i.e., there is no Study Day 0.
Long Term Follow-up Study Day

 The Long-Term Follow Up (LTFU) Study Day of an event (e.g., lab assessment, start date of AE or HIV associated condition) will be derived as the number of days between the date of the event and the end of IP treatment [i.e. max(Last IM Injection Date, Last Oral Bridging End Date)] as follows: 
 If the date of event falls in Long-term Follow up phase, then 
 LTFU Study Day = Date of event - End date of IP + 1
Study Treatment

 Refers to CAB+RPV oral lead-in, CAB + RPV oral bridging, SOC oral bridging, CAB LA + RPV LA

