13.3. Appendix 3: Assessment Windows

13.3.1. Definitions of Assessment Windows for Analyses

Laboratory data, vital signs, ECGs, and genotypic/phenotypic data will be assigned to assessment windows according to actual dates rather than the nominal visit labels as recorded on the eCRF or in the laboratory database.

Prior to visit slotting, assessments are first assigned to a study phase (Screening, Intervention Phase, Extension, or Long Term Follow Up) as defined in Section 13.4.1.

According to the protocol, the nominal target study visit date will be based on the first injection, the Month 1 date. For instance, if Month 1 occurred on July 7th, all subsequent visits are expected to occur on the 7th of each month such that subsequent visits will be August 7th, September 7th, October 7th, etc. Since there are not >28 days in each month of the year, if the Month 1 injection occurred on the 29th, 30th, or 31st of the month, then the target study visit date for the remainder of the visits will be the 28th of the month.

The nominal target study visit day is derived as

- **M1 Target Day** = Date of Actual M1 Injection Visit Date – Date of First Oral lead-in Dose + 1, if subject receives M1 injection; else M1 Target Day = 30.
- **Mx Target Day** = Mx Nominal Target Study Visit Date – Date of First Oral lead-in Dose + 1, for x=2,3, ...

Assessment windows will be derived based on the midpoint between two consecutive planned target study visit dates. For the Snapshot efficacy data, the same approach will be used, except for Month 12, which will use a \pm 6-week window around the projected target study visit date at Month 12.

For parameters which are not scheduled to be assessed at visits, the all-inclusive assessment windows will still be used; however, data summaries will only report scheduled visits. Assessments at unscheduled visits will be included in summaries of worst-case values across visit (e.g. during the intervention phase) and in data listings, as well any algorithms that make use of additional data (e.g., Snapshot).

Table 1 Assessment Windows for Screening, Intervention and Extension Phase Data (Excluding HIV-1 RNA and PK data)

Target (Study Day)	Analysis Window		Analysis Timepoint
	Beginning Timepoint	Ending Timepoint	
Day of earliest record	Assessment Study Day ≤ 1		Screening
For subjects discontinuing prior to receiving first injection:			
30	Assessment Study Day = 2	Study Day of Last CAB/RPV Oral Dose+1	Month 1

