Day of earliest record	Assessment Study Day \leq 1		Screening
	For subjects discontinuing prior to receiving first injection:		
28	Assessment Study Day = 2	Study Day of Last Oral Lead-in Dose +1	Month 1
	Assessment Study Day > (Study Day of Last CAB/RPV Oral Lead-in Dose +1)		Follow-up
	For subjects receiving first injection:		
Date of First Injection	Study Day = 2	M1 target day + $\text{floor}[(M2 \text{ target day} - M1 \text{ target day})/2]$	Month 1
M2 Target Day	M1 target day + $\text{floor}[(M2 \text{ target day} - M1 \text{ target day})/2]$ +1	M2 target day + $\text{floor}[(M4 \text{ target day} - M2 \text{ target day})/2]$	Month 2
M4 Target Day	M2 target day + $\text{floor}[(M4 \text{ target day} - M2 \text{ target day})/2]$ +1	M4 target day + $\text{floor}[(M6 \text{ target day} - M4 \text{ target day})/2]$	Month 4
M6 Target Day	M4 target day + $\text{floor}[(M6 \text{ target day} - M4 \text{ target day})/2]$ +1	M6 target day + $\text{floor}[(M8 \text{ target day} - M6 \text{ target day})/2]$	Month 6
M8 Target Day	M6 target day + $\text{floor}[(M8 \text{ target day} - M6 \text{ target day})/2]$ +1	M8 target day + $\text{floor}[(M10 \text{ target day} - M8 \text{ target day})/2]$	Month 8
M10 Target Day	M8 target day + $\text{floor}[(M10 \text{ target day} - M8 \text{ target day})/2]$ +1	M12 target day - 43	Month 10
M12 Target Day	M12 target day - 42	M12 target day + 42	Month 12
M13 Target Day	Assessment Study Day > M12 target day + 42		Month 13

Target (Study Day)	Analysis Window		Analysis Timepoint
	Beginning Timepoint	Ending Timepoint	
For subjects who permanently discontinue study treatment during the Intervention Phase:			
	Assessment Study Day > Max (Study Day of Last Dose of Oral Study Treatment (CAB+RPV or SOC Bridging) +1, Study Day of Last CAB + RPV Injection + 35)		Follow-up

Table 3 Assessment Windows for Extension Phase HIV-1 RNA Data

Target (Study Day)	Analysis Window		Analysis Timepoint
	Beginning Timepoint	Ending Timepoint	
M13 Target Day	Study Day of Nominal Month 13 Visit	M13 target day + floor [(M15 target day – M13 target day)/2]	Month 13
M15 Target Day	M13 target day + floor [(M15 target day – M13 target day)/2] + 1	M15 target day + floor [(M16 target day – M15 target day)/2]	Month 15
M16 Target Day	M15 target day + floor [(M16 target day – M15 target day)/2] + 1	M16 target day + floor [(M18 target day – M16 target day)/2]	Month 16

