13.4. Appendix 4: Study Phases and Treatment Emergent Adverse Events

13.4.1. Study Phases

AEs will be assigned to study phases as defined in Table 6. Laboratory data (efficacy, safety, and virology), HIV associated Conditions, health outcomes assessments, vital signs, and ECGs will be assigned to study phases as defined in Table 7.

Assessments/events are assigned to study phases sequentially, starting from the top of each table.

Table 6 Study Phases for AEs

Study Phase	Definition
Screen	Date < Intervention Phase Treatment Start Date
Intervention	
For subjects continuing into the Extension Phase: Intervention Phase Treatment Start Date \leq Date < Date of Nominal Month 13 Visit
 
For subjects not continuing into the Extension Phase: Intervention Phase Treatment Start Date \leq Date < LTFU ART Start Date [a]
 
For AEs leading to treatment withdrawal with start date equal to the LTFU ART Start Date, Intervention Phase instead of Long-term Follow-up Phase will be assigned.

Extension Phase	
Date of Nominal Month 13 Visit \leq Date < LTFU ART Start Date [a]
 
For AEs leading to treatment withdrawal with start date equal to the LTFU ART Start Date, Extension Phase instead of Long-Term Follow-up Phase will be assigned.

Long Term Follow-Up	
For subjects who receive at least one CAB/RPV injection and permanently discontinue study treatment: AE Start Date \geq LTFU ART Start Date
 
AEs with completely missing start date:
 
 • If AE end date is \leq Intervention Phase Treatment Start Date, then assign to Screening Phase; • Else if AE end date is completely missing or Intervention Phase Treatment Start Date $<$ AE end date \leq Date of Nominal Month 13 Visit, then assign to Intervention Phase; • Else if AE end date $>$ Date of Nominal Month 13 Visit, then assign to Extension Phase.

Date=AE Start Date

- [a] If participants have missing LFTU ART start date, only the lower bound will be considered in the derivation.

Table 7 Study Phases for Laboratory, PK, ECG, Vital Signs, HIV-1 Associated Conditions, and Protocol Deviation Data

Study Phase	Definition
Screen	Date ≤ Study Treatment Start Date
Intervention	
For subjects continuing into the Extension Phase: Intervention Phase Treatment Start Date < Date < Date of Nominal Month 13 Visit
 
For subjects not continuing into the Extension Phase: Intervention Phase Treatment Start Date < Date ≤ LTFU ART Start Date ^[a]

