Extension Phase	For subjects continuing into Extension Phase: Date of Nominal Month 13 Visit ≤ Date ≤ LTFU ART Start Date ^[a]
Long Term Follow-Up	For subjects who receive at least one CAB/RPV injection and permanently discontinue study treatment: Assessment Date > LTFU ART Start Date

- Date = start or assessment date
- [a] If participants have missing LFTU ART start date, only the lower bound will be considered in the derivation.

Study phase of discontinuation will be determined according to Table 8.

Table 8 Study Phases for Study Conclusion/IP Discontinuation

Study Phase	Definition
Intervention Phase	
For IP Discontinuation: Discontinuation Date is not missing, and no assessments collected at any extension phase nominal visits (e.g. Month 13, Month 15, Month 17 etc.).
 
For Study Conclusion: Discontinuation or Completion Date is not missing, and no assessments collected at any extension phase nominal visits (e.g. Month 13, Month 15, Month 17 etc.) and at any LTFU phase nominal visits (e.g. LTFU Month 3, LTFU Month 6, etc.)

Extension Phase	
For IP Discontinuation: Discontinuation Date is not missing, and assessments collected at any extension phase nominal visits (e.g. Month 13, Month 15, Month 17 etc.).
 
For Study Conclusion: Discontinuation or Completion Date is not missing, and assessments collected at any extension phase nominal visits (e.g. Month 13, Month 15, Month 17 etc.) but no assessments collected at any LTFU phase nominal visits (e.g. LTFU Month 3, LTFU Month 6, etc.)

LTFU Phase	
Not applicable for IP Discontinuation.
 
For Study Conclusion: Discontinuation or Completion Date is not missing, and assessments collected at any LTFU phase nominal visits or has taken any LTFU ART medications (e.g. LTFU Month 3, LTFU Month 6, etc.)

- Discontinuation or Completion Date = date of failure to complete study/date of completing study/date of IP discontinuation

Medication use will be classified as prior and concomitant with study treatment according to Table 9, noting that a medication can be assigned as “taken” during more than one study phase.

Table 9 Study Phases for Non-ART Medications/ART Medications

	Definition
Prior	Medication Taken < Intervention Treatment Start Date

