13.6.3. Efficacy

Efficacy	
Snapshot	

 • The Snapshot algorithm is intended to be primarily a virologic assessment of the endpoint, and as such follows a "virology first" hierarchy. • 'HIV-1 RNA < 50 c/mL' or 'HIV-1 RNA ≥ 50 c/mL' within an analysis window (see Table 2 and Table 3) is typically determined by the last available HIV-1 RNA measurement in that window while the participant is On-treatment in the Intervention Phase (as assigned based on Section 13.3). • When no HIV-1 RNA data is available within a window, a participant cannot be assigned to the category of 'HIV-1 RNA < 50 c/mL'. Depending on the reason for lack of data, the participant will be classified as 'HIV-1 RNA ≥ 50 c/mL' or reported as 'No Virologic Data at Week X'; in the latter case, the algorithm further classifies the nature of the missing data. Typically, a participant withdrawn (i) due to AE or, (ii) for another reason yet was suppressed at the time, will be counted as 'No Virologic Data at Week X'. Should a participant withdraw for reasons other than AE and was not suppressed at the time, they will be categorized as 'HIV-1 RNA ≥ 50 c/mL'. 	

Efficacy

 Full details of the algorithm, including the handling of special cases, are included in Appendix 9: Snapshot Algorithm Details.
Plasma HIV-1 RNA

 For summaries and analyses which use HIV-1 RNA level as a continuous measure, the logarithm to base 10 of the value will be used. HIV-1 RNA results may be provided as censored values, such as <40 or >9,999,999 c/mL. For the purposes of summary statistics, such values will be replaced by the next value beyond the limit of detection, e.g., 39 or 10,000,000 c/mL, respectively, for the given examples. Data listings will show the censored values as provided.
Confirmed Virologic Failure (CVF)

 For the purposes of clinical management in this study, CVF is defined as: 
 Rebound as indicated by two consecutive plasma HIV-1 RNA levels \geq 200 c/mL. The CVF definition is provided in the protocol Section 7.1.3 Only plasma HIV-1 RNA values determined by the central laboratory will be used to assess virologic failure.
CDC Classification for HIV-1 Infection (2014)

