13.9. Appendix 9: Snapshot Algorithm Details

Detailed Algorithm Steps

 Consider an analysis visit window for Month X as defined in Table 2. The HIV-1 RNA threshold of 50 will be analysed, in this study The COVID-19 pandemic presents significant logistical challenges for many clinical sites around the world, with variable restrictions being placed on site resources and operations, and on an individual participants ability to attend clinic visits. The snapshot algorithm is modified to allow for the presentation of full scope of COVID-19 relatedness. The analysis window for 'Month 12' and HIV-1 RNA threshold of '50 c/mL' are used for the purpose of illustration. A participant's Snapshot response and reason at Month 12 are categorized as below. 
 HIV-1 RNA < 50 c/mL HIV-1 RNA \geq 50 c/mL 
 Data in window not below 50 
 Non-COVID-19 related 
 Discontinued for lack of efficacy Discontinued for other reason while not below 50 COVID-19 related 
 Discontinued for lack of efficacy Discontinued for other reason while not below 50 No Virologic Data at Month 12 Window 
 Non-COVID-19 related 
 Discontinued study due to AE or death Discontinued study for other reasons On study but missing data in window COVID-19 related 
 Discontinued study due to AE or death Discontinued study for other reasons On study but missing data in window Change in background therapy*

* Note: Use of CAB + RPV oral bridging and SOC oral bridging medication, where the latter is due to unavailability of CAB/RPV IM injections or oral CAB+RPV during the pandemic, will not be considered a "Change in background therapy" in the Snapshot algorithm. All other permanent changes in ART are not permitted in this protocol.

- The steps in determining response and reasons are indicated in the table below, in the order stated.
- Background therapy is not given to participants while on study. The “change in background therapy” in detailed steps below refers to the “change in ART” in this study.

Detailed steps		
Condition ('Month 12' indicates Month 12 window)	Response	Reasons
1. If non-permitted change in background therapy prior to Month 12	HIV-1 RNA \geq 50	Change in background therapy

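### The fallback for a missed Month 13 visit can set the nominal Month 13 date to the Month 12 visit date, so a measured Month 12 viral load leaves the Snapshot analysis

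*SAP*

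**What the plan says.** SAP 13.6.1 defines the nominal Month 13 visit date in three tiers: the Month 13 injection date; failing that, the date of the latest Month 13 assessment; and, for someone who continues into the Extension Phase but missed the visit, "the nominal Month 13 visit date is defined by the last contact date prior to the date of the first nominal extension phase visit". Its examples of that first extension visit are Months 15 and 17. Last contact is not defined.

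The date is then used as follows.

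- Table 7 in 13.4.1 splits laboratory data by phase. For a continuing participant, Intervention is "Intervention Phase Treatment Start Date < Date < Date of Nominal Month 13 Visit" and Extension is "Date of Nominal Month 13 Visit ≤ Date ≤ LTFU ART Start Date".
- Section 13.3.1 fixes the order of operations: "Prior to visit slotting, assessments are first assigned to a study phase".
- Table 3 in 13.3.1 opens the Extension Month 13 window for HIV-1 RNA at "Study Day of Nominal Month 13 Visit".
- Section 13.6.3 bases the Snapshot result on the "last available HIV-1 RNA measurement in that window while the participant is On-treatment in the Intervention Phase". Section 13.9 begins "Consider an analysis visit window for Month X as defined in Table 2", and Table 2 covers only Screening and Intervention data. Its Month 12 window runs from 42 days before to 42 days after the Month 12 target day.

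**The concern.** The fallback date serves as a phase boundary, and the boundary day belongs to the later phase. If the last contact before the first extension visit is the Month 12 visit, everything dated that day becomes Extension data. Because phase is assigned before windows, a viral load drawn on time at Month 12 cannot reach the Month 12 Snapshot window.

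Tables 2.1 and 2.2, the Month 12 Snapshot outcome summaries, are headline deliverables. A suppressed participant with a valid result would appear there as having no virologic data. A participant at or above 50 c/mL would be moved out of the failure row in the same way.

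**Working it through.** **The rule, step by step.** Take a participant who attends Month 12, has no Month 13 injection or assessment, has no contact recorded until the first attended extension visit, and continues.

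1. 13.6.1, third tier: nominal Month 13 date = Month 12 visit date.
2. Table 7: Intervention needs a date strictly before the nominal Month 13 date. The Month 12 date equals it, so the viral load is Extension.
3. Table 3: the Extension Month 13 window opens that day, so the viral load is labelled Month 13.
4. 13.6.3 and 13.9: Snapshot looks for an Intervention Phase value in the Table 2 Month 12 window, and this one is excluded.
5. 13.9, step 3.2.1: the participant is still on study with no on-treatment value in the window, and is classed as on study with missing data.

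**Can the Month 10 viral load fill the window?** Month 10 is the previous scheduled HIV-1 RNA. Use the SAP's example of a first injection on 7 July, and assume oral dosing began on 7 June 2019.

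- Month 10 target (7 April 2020) = study day 306.
- Month 12 target (7 June 2020) = study day 367.
- Window opens on 367 − 42 = day 325.
- 367 − 306 = 61 days, so Month 10 falls outside.

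Two calendar months span 59 to 62 days. With visits up to 7 days either side of target, the Month 10 sample lies 59 − 7 = 52 to 62 + 7 = 69 days before the Month 12 target, always beyond 42.

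**Check over many schedules.** I applied Tables 2 and 7 and the 13.6.1 rule to 365 start dates, with first injection on study day 30 (assumed) and Month 10 and Month 12 samples each at target −7 to +7 days: 365 × 15 × 15 = 82,125 schedules.

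| Nominal Month 13 date | Schedules with no Month 12 Snapshot value |
|---|---|
| Month 13 attended on target | 0 |
| Last contact = Month 12 visit | 82,125 (100%) |
| Last contact = day after Month 12 visit | 0 |
| Last contact = Month 14 | 0 |

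**Can the COVID-19 LOCF repair it?** Section 13.7.2.2 imputes only values missing for COVID-19 reasons. This value was measured, so it does not qualify. If LOCF were applied anyway, an older result would replace a real Month 12 result.

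**Size.** N = 115 (SAP 2.3). One affected suppressed participant costs 1/115 = 0.87 percentage points. For illustration, assume 109/115 are truly below 50 c/mL. Limits are Clopper-Pearson.

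| Affected (assumed) | Count | Proportion (95% CI) |
|---|---|---|
| 0 | 109/115 | 94.8% (89.0–98.1) |
| 1 | 108/115 | 93.9% (87.9–97.5) |
| 3 | 106/115 | 92.2% (85.7–96.4) |
| 5 | 104/115 | 90.4% (83.5–95.1) |

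The SAP gives neither the true proportion nor the number affected.

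**The case against.** A reader might infer that the Month 12 visit is normally the last contact, so that anyone who misses Month 13 is lost. The SAP does not support this.

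- Nothing limits a contact to a clinic visit. The schedule in 13.2.1.1 marks a visit reminder contact at every visit, and any contact recorded one day or more after Month 12 removes the problem.
- The rule's examples of the first extension visit are Months 15 and 17, and Table 8 lists Months 13, 15 and 17. If Month 14 is not counted, someone who returns at Month 14 has that visit as the last contact, and the Month 12 data stay in place.
- The fallback is the third tier. Any Month 13 assessment, even without the injection, avoids it.

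A reader might also infer broad damage to laboratory and adverse event reporting. Table 1 uses one set of windows across Intervention and Extension for everything except HIV-1 RNA and PK, and section 8 combines the two phases in safety displays unless the title says otherwise. Those summaries are largely untouched.

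Finally, efficacy is secondary and descriptive (2.4 and section 7), and Listings 9 and 10 would let a careful reader spot a misassigned case.

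These points narrow the problem without removing it. The Month 14 reading is itself uncertain: injections continue monthly after Month 12, Table 4 gives Month 14 its own row under Intervention and Extension, and the amended RAP presents the Month 15 and 17 list as examples where the original RAP presented it as exhaustive. On any reading, a participant who misses both Months 13 and 14 with no recorded contact, and then continues, is caught. A listing that exposes an error does not correct the headline table.

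**Conclusion.** The rule is faulty at its boundary. It misclassifies the Month 12 viral load when four conditions hold: the participant continues into Extension; there is no Month 13 injection or assessment; no contact is recorded between the Month 12 visit and the first attended extension visit; and no other on-treatment viral load lies in the Month 12 window before that visit. When they hold, the loss is certain.

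The cost is 0.87 percentage points per affected suppressed participant with N = 115. The tabulated counts of one to five are assumptions, and the true count may be zero. The damage is mainly to the Intervention Phase Snapshot displays, including Tables 2.1 and 2.2. It also reaches the few adverse event displays labelled Intervention Phase, such as the Month 12 versions of Figures 3.1 and 3.2, where reactions starting on or after the Month 12 injection date would drop out.

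**What to change.** In 13.6.1, define last contact date, including whether telephone or reminder contacts count. Require the fallback nominal Month 13 date to be at least one day after the actual Month 12 visit and no later than the first attended extension visit, and state whether Month 14 is an extension visit for this purpose. Alternatively, state in 13.4.1 that nominal Month 12 visit data always belong to the Intervention Phase.

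Either is a sentence of text and a small change to the date derivation, with no new data. In the schedules checked, moving the date to one day after the Month 12 visit kept the Month 12 viral load in all 82,125.

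The projected Month 13 target date is a less clean substitute. It falls about 30 days after the Month 12 target (day 397 against 367 in the example), while the Snapshot window runs to +42, so a retest from about day +30 to +42 would go to Extension.
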